9.3.1 Primary Endpoint Analysis

Frequencies, percentages and two-sided 95% CIs will be calculated for the primary endpoints for the entire study population and for selected subgroups.

9.3.1.1 Self-Selection: Proportion of self-selection population who make a correct selection decision regarding use of the product.

The first primary endpoint is the proportion of those subjects making the self-selection decision who make a correct decision about whether the product is right for them to use.

9.3.1.1.1 Populating the Self-Selection Table

Each participant will be classified on two key variables: (1) whether they are a selector and (2) whether their use of the product would be appropriate, in order to populate the typical 2x2 self-selection table.

Selection Decision: The selection phase of the interview consists of the self-selection question and purchase (or equivalent) question, with accompanying neutral follow-up questions. All subjects who go on to purchase/obtain the study product will be categorized as selectors. Subjects who do not eventually complete the purchase/dispensing of the product will be classified as a selector or a non-selector primarily on the basis of the initial self-selection and purchase questions (the second selection decision will be included for those with a positive enrollment pregnancy test). However, all information recorded during the selection phase of the interview, including verbatim responses to open-ended follow-up questions, will be considered in the classification of participants as selectors or non-selectors. Participants who offer

modifying information in open-ended responses to neutral probing will be re-categorized accordingly. For the subset of subjects that select the product, report not being pregnant, sign consent, and then receive a positive result from the subsequent enrollment pregnancy test, a second selection question will be asked. Their classification as a selector or non-selector will take into account this second selection decision made in light of new health status information.

Appropriate to Use:

Non-selectors will be classified on the variable Appropriate for Use as follows:

Yes: meets the label criteria for use, representing those who could have selected appropriately, but did not (**Cell C**).

No: does not meet the label requirements for use, and appropriately did not select (**Cell D**). This includes those participants who otherwise might have met the strict criteria for appropriate use according to the DFL, but who give a medically appropriate rationale for their non-selection decision. For example, if a participant who otherwise meets the labeled criteria for use does not select the product and cites the fact that they have unexplained vaginal bleeding between their menstrual periods as their reason for not selecting (which otherwise does not disqualify a subject from using, but rather suggests that they talk to a doctor), that participant will be re-classified from Cell C to Cell D. A physician will review the casebook for each participant who falls into Cell C to determine if any participants meet that criterion.

Selectors will be classified on the variable Appropriate for Use as follows:

Yes: either meets the strict label criteria for use (1-Correct Selectors) or reported and measured characteristics justify the selection decision (2-Acceptable Selectors), representing those who chose to use the product who made a clinically acceptable decision despite not meeting the strict label criteria for use (**Cell A**).

No: does not meet strict label criteria and reported and measured characteristics do not justify the selection decision (3-Incorrect Selectors), representing those who chose to use the product, but should not have (**Cell B**).

Further definitions of Correct, Acceptable, and Incorrect Selectors follow:

- 1) Correct Selectors. Participant meets the strict criteria of the DFL, including:
 - a) No absolute contraindications (not male, no history of any cancer, not pregnant, does not have a known allergy to one of the ingredients)
 - b) Is a woman of childbearing potential? This would include all women who do not report any of the following: surgical sterilization (tubal ligation, hysterectomy, or bilateral oophorectomy) or postmenopausal for at least one year.
- 2) Acceptable Selectors. Participant does not meet the strict criteria of the DFL, but selection is classified as appropriate because they are judged clinically (see Section 8.5.3) to be an appropriate selector. This group is

expected to be quite small and might include for example: a woman who has a history of breast cancer, but who reports that she has been told by a healthcare provider that her cancer is not hormone sensitive and she can use oral contraceptives.

- 3) Incorrect Selectors. This group includes selectors who are not correct or acceptable, including having any of the following:
 - a) An absolute contraindication to the product (has a history of any cancer, is pregnant and intends to use while pregnant, and/or has a known allergy to one of the ingredients)
 - b) Is a man
 - c) Is a woman without childbearing potential? This would include all women who report any of the following: surgical sterilization (tubal ligation, hysterectomy, or bilateral oophorectomy) or postmenopausal for at least one year.

Please note that the criteria upon which initial selection is judged include the absolute contraindications. Two conditional contraindications from the prescription labeling are presented in other sections of the DFL to reflect their conditional nature, namely, unexplained intermenstrual bleeding and liver problems. The fact that these two warnings are conditional rather than absolute (i.e. they are "ask a doctor before use" warnings rather than "do not use" warnings) means that consumer behavior relative to these warnings cannot be evaluated as part of the initial self-selection decision, because correct behavior depends on subsequent actions (asking a doctor), and initial selection is not necessarily inappropriate if the subject does select to use the product but indeed follows those instructions to talk to a doctor about use of the medicine. Evaluation of the instructions regarding those two messages will be done individually based on the complete subject behavior in discrete endpoints.

9.3.1.1.2 Analyzing the Self-Selection Table

Cell A represents a correct decision, namely consumers for whom the study product is right to use who choose to use it, and therefore presents very little potential adverse clinical consequences.

Cell C, while not technically correct, is a decision that accrues no health risk, but rather is a missed opportunity to use the drug. Thus, these participants are considered neither correct nor incorrect and are usually left out of the primary self-selection analysis.

The most critical self-selection decision is made by participants who, based on their health status, should not use the study medication (cells B and D). Unlike an incorrect decision by consumers for whom this product is appropriate (cell C), an incorrect decision (cell B) by these consumers who should not use the medicine has potential efficacy or safety implications. Because it is expected that very few subjects will be inappropriate for use, this endpoint will be measured by the following proportion, taken from the self-selection table [(cell A + cell D)/(all subjects)].

Other proportions will also be presented, including the total correct selectors as described by the equation [(cell A + cell D)/(cell A + cell B + cell D)] (excluding cell C)

and the typical self-selection metric, namely the proportion described by the equation [cell D/(cell B + cell D)]. This proportion represents a correct non-selection decision. In other words, this is the proportion of those who should not select the product who correctly do not select.

9.3.1.2 Actual Use: Use of the study medication every day

This is adherence to the instruction to take one tablet every day, and is measured as the proportion of active dosing days among the user population (all subjects who take at least one dose of the IP) where a dose was taken (excluding days after a subject discontinues use of the IP—defined as the point at which no additional doses are taken). Specifically, to be included in the numerator (representing appropriate adherent use), a dosing day must meet one or more of the following criteria:

- 1. A tablet must be taken at some time during the dosing day.
- 2. Subject reports using a condom (or another barrier method) for any act of intercourse or abstaining from intercourse.

Regarding #2 above, the DFL provides explicit instructions for consumers when they miss pills which mitigate any risk of pregnancy related to that missed pill. So, while overall adherence to the daily dosing schedule will be presented as well (without accounting for secondary barrier method use for acts of intercourse or for abstinence), the overall measure of adherence will allow for those label-directed or appropriate consumer behaviors. Please note that for the purposes of this endpoint, diary data will serve as the primary source of data, with interview data collected by telephone used to supplement only in cases where diary data may be missing.

9.3.1.3 Actual Use: Use of the study medication at the same time of day

This endpoint is the proportion of active dosing days among the user population (all subjects who take at least one dose of the IP) which demonstrate adherence to the labeled directions for use related to the time of day the study medication is taken (excluding days after a subject discontinues use of the IP). Specifically, to be included in the numerator (representing appropriate adherent use), a dosing day must meet one or more of the following criteria:

- 1. For all dosing days where a tablet was taken the preceding day, the tablet is taken no later than 27 hours after the previous tablet (representing 24 hours from last dose plus three hours, consistent with the DFL instructions).
- 2. Subject reports using a condom (or another barrier method) for any act of intercourse or abstaining from intercourse.

Again, regarding #2 above, the DFL provides explicit instructions for consumers when they are late taking their pill which mitigates any risk of pregnancy related to that late dose. So, while overall adherence to taking the product at the same time every day will be presented as well (without accounting for secondary barrier method use for acts of intercourse or for abstinence), the overall measure of adherence to dose timing will allow for those label-directed or appropriate consumer behaviors. Please note that for the

purposes of this endpoint, diary data will serve as the primary source of data, with interview data collected by telephone used to supplement in cases where diary data may be missing.

9.3.1.4 Actual Use: Use of the study medication without an extended break or any break between packs

While another endpoint measures all instances of any missed pills, this endpoint is intended to capture the special cases in which any subjects take an extended break from daily pill taking for any reason at any time, including. subjects who miss any pills between packs. For example, there may be subjects who do not appreciate the difference between a COC (where a medication break during menstruation is common) and the IP instructions which call for use daily without any breaks. This concept is measured as the proportion of the user population who do not take an extended break or a break between packs (where a single pack is defined as 28 tablets). A "break" is distinguished from discontinuation (defined above), which is a consumer choice not proscribed by the label.

The numerator will comprise the total user population minus those subjects who miss taking the IP for seven consecutive days on at least one occasion OR for four consecutive days or more on at least two occasions during active use of the product OR who take any break between packs (including missing one pill between packs), as recorded in their medication use diary. Subjects with a qualifying use pattern will be asked directly about that use during the next scheduled follow-up telephone interview. Please note that missed pills that are not included this endpoint are accounted for in another primary endpoint. Also note that for the purposes of this endpoint, diary data will serve as the primary source of data, with interview data collected by telephone used only to supplement in cases where diary data may be missing.

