- E. Actual Use: Proportion of user population who experience one of the "Talk to a doctor" conditions listed within the "When using this product" or "Stop use and ask a doctor" sections of the label who report contacting a healthcare provider and/or stop use as directed by the label
- F. Actual Use: Number of pregnancies reported during the course of the study

Other Measures

- A. Actual Use: Character and frequency of adverse events as reported by the user population
- B. Actual Use: Patterns of use, including discontinuation rates and reasons for discontinuation
- C. Actual Use: Proportion of user population who experience severe vomiting or diarrhea within 4 hours of taking their daily pill who report using a barrier method of contraception every time they have sex (or abstain from intercourse) for the next 48 hours
- D. Actual Use: Characterize healthcare seeking behavior among subjects

Study Design

This is an observational open-label, multi-center, 16-week study designed to mimic an OTC-like environment in which consumers will make a selection (and purchase decision, in the case of pharmacy sites) about the product based on their reading of the DFL and other information on the outer package, and then, if they choose to, take Opill® home and use the product aided by the OTC labeling (DFL, Consumer Information Leaflet (CIL) and reminder card). The study will increase understanding regarding how consumers will use the medication in an OTC-like environment.

Number of Participants

A total of approximately 900 subjects will be allowed to proceed to the use phase of the study. Assuming that about 80% of those who proceed to the use phase will both use the study medication and participate in at least one follow-up telephone call that will yield an actual use population of approximately 720 subjects among which to evaluate the primary endpoints. In an effort to achieve an adequate subgroup of adolescent users (age 12-17), adult purchasers will be constrained to no more than 725. Efforts will be made to enroll an adolescent subgroup of approximately 175 use phase participants (or more, should a higher proportion naturally occur). Additionally, among adolescents, a sample of 50 use phase subjects age 12-15 will be sought.

Methods

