9.1 Sample Size Determination

For the purposes of this AUT, sample size has been set at approximately 900 purchasers (use phase participants). Given that subjects are responding to recruitment aimed at those interested in an OTC birth control medicine, most subjects who choose to purchase the study product are expected to actually use the product during the study.

Assuming approximately 900 purchasers, if 80% of those purchasers use the product within the study period, that would yield an actual user population of approximately 720. Allowing for a further 20% loss to follow-up would yield a measurable user population of approximately 576.

Because AUTs are not hypothesis-testing comparative trials, study sample size is designed to allow for adequate evaluation of key endpoints across all participants and among several subgroups. As the analysis of AUTs typically focuses on estimating the proportion (and associated 95% confidence intervals) of individual endpoints, sample size is most often based on the number of participants needed to constrain the confidence interval (CI) to a limited range. As an illustration, for this study, assuming an 85% correct behavior to any single endpoint (of course, the CI depends on the actual point estimate and will be calculated based on the data), a sample of 720 participants would constrain the CI to ±2.8%. Table 5 provides the 2-sided 95% CI for various sample sizes around a point estimate of 85%.

Table 5 Two-sided 95% CIs for Various Sample Sizes Around 85% Point Estimate

	N=900 ^a	N=720 ^b	N=576°	N=135 ^d
95% CI around a point estimate of 85%	+/-2.5%	+/-2.8%	+/-3.2%	+/-7.2%

^a Purchasers

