9.3 Endpoint Analysis

A summary of the disposition of subjects (including those who respond to advertisements, the screening and self-selection populations, purchasers, and users)

^b User population (allowing for 20% non-users)

^c User population (allowing for 20% loss-to-follow up)

^d Low literacy subjects

and reasons for exclusion from these populations will be provided. Demographic characteristics, medical history and other background information will be summarized for the self-selection, purchaser, and user populations.

Frequencies and percentages will be presented for categorical data, mean, standard deviation (SD); median, and range will be presented for numerical data.

Frequencies, percentages and 2-sided 95% CI will be calculated for the primary and secondary endpoints using the exact method, without using assumptions or approximations based on distributions. For the primary endpoints, it will be concluded that the established target threshold is reached if the lower limit of the CI of the point estimate is equal to or exceeds the value of the pre-determined threshold.

Endpoints and demographics will be presented for subgroups of interest, with participants dichotomized on the corresponding variables, which include (but are not necessarily limited to) literacy, gender, age (adolescent vs. adult women), and history of previous hormonal birth control use.

A more detailed description of planned data analysis procedures will be found in the Statistical Analysis Plan (SAP) which will be approved and signed before the database is locked.

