9.3.2 Target Thresholds

Objective target thresholds will be set for all the primary endpoints. The objective will be considered met for these endpoints if the lower bound of the 2-sided 95% CI for each endpoint meets or exceeds the established threshold. Target thresholds and a summary of the associated rationale follow.

9.3.2.1 Self-Selection: Proportion of self-selection population who make a correct selection decision regarding use of the product.

HRA proposes to test this message as a primary endpoint because it is the self-selection phase of the study that will determine appropriate use of the product based on the DFL. This endpoint measures several relevant messages in the label:

Use:

For daily use by women to prevent pregnancy

Allergy alert: Do not use if you are allergic to this product or any of its ingredients. Do not use:

· f

if you are male

- if you have ever had any cancer
- if you are already pregnant or think you may be pregnant

This endpoint addresses both correct selection to use in order to prevent unintended pregnancy but also measures appropriate de-selection among individuals who should not use this product.

Do not use if you are male. This contraceptive pill is not intended for use by men. Use by a man would represent a fundamental misunderstanding of the product and its indication. Use by men is very unlikely: National Health and Nutrition Examination Survey (NHANES; 2011-2012) data showed no evidence of men of any age taking oral contraceptive pills³. However, if a man were to take a POP, it is unlikely to have serious clinical consequences. A variety of different progestogens, in a variety of doses and routes of administration, have been tested as hormonal contraceptives for men. Testosterone alone is effective but adding progestin results in an increased rate and extent of suppression⁴. High doses of progestins suppress endogenous production of gonadotrophins and testosterone thereby inhibiting spermatogenesis. Common side effects include acne and changes in mood and libido which are rarely severe enough to lead to discontinuation. Suppression of spermatogenesis is reversed when the treatment is stopped⁵.

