## 4.3 Handling of Missing Data

Missing data will not be imputed; the statistical analyses will be based on cases with relevant data available. For endpoint calculations, if missing data makes it so a case (subject or a dosing instance) cannot be classified as to whether or not it belongs in the numerator, that case will also be excluded from the denominator. All missing data will be flagged, and a reason for why the data are missing will be described in a footnote in each applicable statistical table.

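### Do primary endpoints B and C, proportions of dosing days judged by an exact CI with no stated n, need a clustered interval written into the plan?

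*Protocol*

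**What the plan says.** Endpoint B is "measured as the proportion of active dosing days among the user population" on which a dose was taken, leaving out days after discontinuation; C uses the same denominator with a 27-hour limit (Protocol 9.3.1.2 and 9.3.1.3). For both, a day without a timely tablet still counts as adherent if the "Subject reports using a condom (or another barrier method) for any act of intercourse or abstaining from intercourse". Endpoint D has a different unit: it is "measured as the proportion of the user population who do not take an extended break or a break between packs" (9.3.1.4).

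One rule covers all primary endpoints. Protocol 9.3 says a "2-sided 95% CI will be calculated for the primary and secondary endpoints using the exact method", and 9.3.2 treats the objective as met if "the lower bound of the 2-sided 95% CI for each endpoint meets or exceeds the established threshold". The threshold is 85% for B and 80% for C. SAP section 6 names the method as binomial Clopper-Pearson.

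The documents point two ways on the n for B and C. SAP 4.3 removes a case from the denominator when missing data mean that "a case (subject or a dosing instance) cannot be classified as to whether or not it belongs in the numerator", which fits days. The Protocol Summary expects "an actual use population of approximately 720 subjects among which to evaluate the primary endpoints", and 9.1 illustrates precision "assuming an 85% correct behavior to any single endpoint" with 720 participants and ±2.8%, which fits women. Neither document mentions a clustered variance, a per-woman summary, an intraclass correlation (ICC) or a design effect.

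SAP section 1 reports that the study was terminated shortly after it began because of e-diary problems. SAP 6.2.1 to 6.2.3 then limit the analysis to safety: the number of pregnancies (secondary endpoint F) and adverse events (other measure A).

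**The concern.** An exact binomial interval assumes independent trials. Days from the same woman are not independent: some women are regular pill-takers and some are not. The statement in Protocol 9.3 that the exact method needs no distributional assumptions does not cover this. If an analyst pooled the days and put their total into Clopper-Pearson, the interval would be far too narrow and a result just above 85% or 80% would be declared a success too readily. If another analyst used women as n, as 9.1 does, the bar would be more than two points higher. The same estimate could pass or fail on a choice the protocol does not record, for two of the four primary endpoints of a study meant to support a switch to over-the-counter sale.

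**Working it through.** **Inputs from the documents.** 720 users, or 576 after loss to follow-up (Protocol 9.1); 16 weeks, so at most 112 days per woman; thresholds 85% and 80%; two-sided 95% exact limit. **Assumed, not in the documents:** the ICC, and in the simulation the spread of days per woman and a beta-binomial form.

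**1. The plan's own figure.** The distance from 85% down to the Clopper-Pearson lower limit, with women as n, is 2.50 points (n = 900), 2.82 (720), 3.18 (576) and 7.16 (135). Table 5 gives 2.5, 2.8, 3.2 and 7.2, so it reproduces, and its unit is the woman.

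**2. Pass marks under each unit** (smallest estimate whose lower limit reaches the threshold):

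| n | B, 85% | C, 80% |
|---|---|---|
| 720 women | 87.64% (631/720) | 83.06% (598/720) |
| 720 × 112 = 80,640 days | 85.25% | 80.28% |

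This gap needs no assumed ICC.

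**3. Chance of passing with true adherence at the threshold, days as n.** With 112 days per woman the design effect is DEFF = 1 + 111 × ICC, and the pass probability is about 1 − Φ(1.96/√DEFF).

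| ICC | DEFF | Formula | Simulated B | Simulated C |
|---|---|---|---|---|
| 0.01 | 2.11 | 8.9% | 8.1% | 8.3% |
| 0.05 | 6.55 | 22.2% | 21.5% | 22.0% |
| 0.10 | 12.1 | 28.7% | 28.5% | 27.5% |
| 0.20 | 23.2 | 34.2% | 33.3% | 33.6% |
| 0.30 | 34.3 | 36.9% | 37.1% | 36.6% |

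The simulation had 720 users with 28, 56, 84 or 112 days (probabilities 0.1, 0.1, 0.1, 0.7; mean 95.2, so about 68,500 days). With every user at 112 days, the simulated range is 8.6 to 37.7%. A limit clustered by woman brings the rate back to about 2.5 to 3.4%.

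**4. How local the effect is.** Take B one point below threshold at ICC 0.30: the standard error is √(0.84 × 0.16 × 34.3 / 80,640) = 0.76 points. The pass mark is 1.25 points away, z = 1.65, so the chance of passing is about 5%. For C, √(0.79 × 0.21 × 34.3 / 80,640) = 0.84 points and z = 1.28/0.84 = 1.52, about 6.4%. At ICC 0.5 the simulated figures are 10.6% (B) and 12.5% (C) one point below, and 1.2% and 1.8% two points below.

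**5. Whether the planned size was enough.** For 720 women at 85%, the clustered half-width is 0.63 points at ICC 0.05, 0.86 at 0.10, 1.44 at 0.30 and 1.85 at 0.50. With equal days, women as n is the case ICC = 1, because DEFF is then 112 and 80,640/112 = 720. Table 5 is therefore a cautious illustration for B and C.

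**6. Where B and C might lie.** A day fails B only if the tablet is missed and intercourse is unprotected. The diary figures in 9.3.2.2, 1.0 to 1.2 missed pills per cycle, give 1 − 1.0/28 = 96.4% to 1 − 1.2/28 = 95.7% before that allowance (94.3% for 1.2 pills over an assumed 21-day cycle). At the highest monitored figure, 4.7/28 = 16.8% of days are missed, and B falls to 85% only if 0.15/0.168 = 89% of those days had unprotected intercourse (67% over 21 days). For C to fall to 80%, read day by day, at least 20% of active days must be both untimely and unprotected. The documents give no frequency of intercourse, so the position of C is unknown.

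**7. What is analysed.** SAP 6.2.1 to 6.2.3 leave no output that uses B, C, their intervals or their thresholds.

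**The case for a change.** The best case for a change is that termination removed the analysis but left a published rule with a real ambiguity. Two competent analysts could follow Protocol 9.3 and disagree on any B estimate between 85.25% and 87.64%, or any C estimate between 80.28% and 83.06%. The final SAP repeats the participant-based precision table and the binomial method, so anyone reusing these documents inherits the gap. Even an ICC of 0.01 roughly triples the nominal 2.5%. Nothing shows C to be far from 80%; 9.3.2.3 expects tablets outside the three-hour window to be common. The remedy would take a few sentences.

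Most of this stands as description: the unit is unstated, and the arithmetic is right under the day-level reading. Three things limit it. First, the inflation belongs to one of two open readings, and the only text that attaches a sample size to the primary endpoints counts women, which makes the rule conservative. Second, Protocol 9 and 9.3 left detailed methods to a SAP due before database lock, where a statistician would ordinarily settle the unit and variance; the study ended before that was needed. Third, reuse elsewhere is not a decision of this trial.

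The reassurance about B also has limits. The figure of about 94 to 96% depends on diary reports from combined-pill users whom 9.3.2.2 expects to do better than average, so it is not a floor.

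**Conclusion.** The gap is real but closing it gains nothing here. On the day-level reading, the rule would pass about 8 to 38% of the time at the threshold instead of 2.5% (ICC 0.01 to 0.30), and at most about 7% one point below within that range; at ICC 0.5 the latter rises to about 12%. With women as n it errs toward failing. These rates rest on assumed ICCs, an assumed spread of days and a beta-binomial model. The pass marks and the check of Table 5 rest on the documents alone.

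The final SAP no longer estimates B or C or tests them against a threshold, so naming the unit or clustering the variance would alter no table and no conclusion of this trial, and the planned size was adequate on either reading. Anyone carrying the rule into another study should settle there whether days or women are counted, and cluster by woman if days are; that is a note for the later study, not a change to this plan.
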